17.9 Adverse Event Collection Timeframe

AEs will be collected and evaluated from Baseline (Treatment Day 1), after the first dose of SCY-078 study drug, and SOC voriconazole and through the end of the study. All AEs reported by the subject or observed by members of the clinical staff will be evaluated by the principal investigator (PI) or qualified designee. The PI will attempt, if possible, to establish a diagnosis based on presenting signs and symptoms. The nature of the AE, time of onset relative to study drug administration, duration, severity, and relationship to treatment should be determined. Details of any corrective treatment must be recorded in the eCRF. The PI will determine whether any changes have occurred in baseline signs and symptoms. All AEs and SAEs will be collected in the eCRF.

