11.1.1.4 End of Treatment (EoT)

Subjects will receive study treatment for a maximum duration of 13 weeks. At EoT, subjects will undergo safety procedures and clinical, radiological and mycological assessments for the determination of efficacy outcomes. EoT procedures should also be performed for subjects who discontinued from study treatment before the EoT visit.

11.1.1.5 6-Week Follow-Up (6 Weeks After EoT)

A FU visit will be conducted 6 weeks after the EoT visit to assess recurrence and to conduct a final safety assessment.

11.1.1.6 Visits on Treatment Days 42 and 84

Visits will be conducted on Days 42 and 84 to assess clinical, mycological and radiological outcomes as determined by an independent DRC. In addition, patient-reported outcomes (Karnofsky scale) will be scored.

Survival will also be assessed at these visits. These can be conducted as in-person visits or phone contacts and will document subject status (alive or deceased) and relationship to the IPA. If subject is deceased, the date of death and the investigator's assessed relationship to the fungal infection will also be recorded. If an autopsy is conducted, key findings should be collected in the eCRF.

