11.3 Study Duration/End of Study

Each subject is expected to complete the study, including all FU and Survival visits, within approximately 132 days. The end of study is when the last visit of the last subject occurs.

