15.23 Survival

Survival will be determined on Day 42 and Day 84 (42 and 84 days after Baseline [Treatment Day 1] [first dose of study drug] for randomized subjects and 42 and 84 days after the ICF is signed for screen failures). This can be an in-person visit or a phone contact, and will document subject status (alive or deceased). If subject is deceased, the date of death and the investigator's assessed relationship to the fungal infection will also be recorded. If autopsy is conducted, key findings should be collected in the eCRF.

See Section 19.7 for a detailed description of efficacy outcomes.

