Assessment of	×	2	· · · · · · · · · · · · · · · · · · ·				2			v	
Recurrence										А	
Study Drug Dispensing	а.	X						Х			
Study Drug Dosingt		X			la cia cia cia cia				X		
Study Drug Collection											
and Compliance		X							Х		
Evaluation			.						-		
Subject Diary											
Dispensing, Collection	Х							X	X		
and Review ^u											
Prior and Concomitant	X	X	x	x	х	X	x	x	x	x	x
Medication Review	66	1000		2000	1997	**	 			1942	
Adverse Event Monitoring		x	х	х	Х	х	x	х	х	х	х

Abbreviations: AE=adverse event; applic.= applicable; BAL = bronchoalveolar lavage; BID = twice daily; ECG=electrocardiogram; eCRF = electronic case report form; EoT=end of treatment; GM = galactomannan; PK = pharmacokinetic(s), QD = once daily; TD = Treatment Day; TDM = therapeutic drug monitoring; VFA = visual function assessment.

Visit	Screening Period	Baseline (Treatment Day 1)	Treatment Day 3	Treatment Day 5	Treatment Day 7	Treatment Day 10	Treatment Day 14	Every 14 days during treatment ^a	EoT ^b	6-Week FU (6 weeks after EoT)	Unscheduled Visits
Days (allowable window)	Day -4 to Day -1 ^c	0	+1	+1	+1	+1	+1	± 2 days	±1 day	± 2 days	
Procedure											

a. Antifungal treatment duration will be for a recommended minimum of 6 weeks and a maximum of 13 weeks.

b. All EoT procedures should be performed for subjects who discontinue from study treatment before the EoT visit.

c. The Screening Period and Baseline/Treatment Day 1 visits may be combined.

d. An overall assessment and questions to investigate visual acuity, visual field and color perception should be conducted by the Principal Investigator or designee during Screening or at Baseline and again at approximately Treatment Day 28 (if voriconazole treatment continues beyond 28 days). An ophthalmologist exam is recommended if there are clinically significant visual function abnormalities identified during the general physical exams at or after Baseline. An ophthalmologist exam is not required for the enrollment of patients into the study but should be conducted as early as possible, if clinically significant visual function abnormalities. Additional evaluations of visual function may be conducted as needed, at the investigator's discretion. Any visual disturbance identified should be documented either as part of the subject's medical history and/or as an AE, accordingly.

- e. A 12-lead ECG will also be performed once between Days 7 and 21.

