s. Samples for SCY-078 PK will be collected from all subjects. For the first 20 randomized subjects, blood PK samples will be collected predose on Treatment Days 1, 3, 7 and 14, approximately within 1 hour before dosing, and at 2-4 hours and 6-8 hours after dosing on Treatment Days 1, 7 and 14. The PK data from the first 20 subjects will be assessed in an interim PK analysis. For subjects subsequently randomized, blood PK samples will be collected predose on Treatment Days 1, 3, 7 and 14, approximately within 1 hour before dosing, and at 4-8 hours after dosing on Treatment Days 1, 7 and 14. The time of dosing and sample collection must be recorded in the eCRF and on the subject's medical record.

t. All randomized subjects will receive either SCY-078 + voriconazole or SCY-078 placebo + voriconazole.

u. For non-hospitalized patients only.

PROCEDURE Visit	Visit/contact Survival Day 42	Visit/contact Survival Day 84
Days (allowable window)	± 2	± 4
Assessment of treatment outcome	Х	x
Subject Status (alive/ deceased)	X	x
Karnofsky Score	X	x

Table 5Schedule of Treatment Visits and Procedures forDays 42 and 84(Study SCY-078-206)

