10.3. Adverse Events

Adverse events will be coded into SOCs and PTs using the MedDRA 26.0 .

If the relationship to a study drug is missing then in the summary tables the AE will be classified as related. Similarly, missing severity will be classified as severe in the summary tables.

Treatment-related AEs will be those with relationship to either ibrexafungerp or voriconazole of related.

Summary tables of AEs will be based on treatment emergent adverse events (TEAEs).

A TEAE is defined as any event not present prior to the initiation of the study treatment, or any event already present which worsens either in intensity or frequency following the exposure to the study treatment.

AEs with incomplete start dates will be considered as TEAE if:

- Day and month are missing and the year is equal to or after the year of the first dose date
- Day is missing and the year is after the year of the first dose
- Day is missing and the year is equal to the year of the first dose date and the month is equal to or after the month of the first dose date
- Year is missing
- Complete start date is missing.

For summaries by SOC and PT, a subject will be counted once at the SOC level and once at each PT within the SOC level. For summaries by SOC, PT and maximum severity, a subject will be counted once at the highest severity for which an event occurred at the SOC level and the highest severity for each unique PT within that SOC level. Therefore, subjects may only contribute once to each PT and once to each SOC level.

An overall summary of TEAEs will be provided showing the number and percentage of subjects reporting TEAEs, treatment-related TEAEs, TEAEs with severe severity, TEAEs leading to withdrawal of study treatment, serious TEAEs and treatment-related serious TEAEs, TEAEs leading to Death.

The following TEAE tables will also be provided:

- A summary of TEAEs overall and by SOC and PT
- A summary of treatment-related TEAEs overall and by SOC and PT
- A summary of TEAEs by maximum severity, overall and by SOC and PT
- A summary of TEAEs leading to withdrawal of study treatment, overall and by SOC and PT
- A summary of serious TEAEs, overall and by SOC and PT
- A summary of treatment-related serious TEAEs, overall and by SOC and PT
- A summary of TEAEs leading to Death, overall and by SOC and PT

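### The end of AE collection is stated inconsistently and, under the visit schedule, moves with EoT; SAP 10.3 tabulates crude TEAE percentages with no common window

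*Protocol*

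**What the plan says.** Protocol 17.9, with 15.29 and the synopsis, starts AE collection after the first dose and runs it "and SOC voriconazole and through the end of the study". Section 11.3 fixes that end for the trial as a whole: "The end of study is when the last visit of the last subject occurs". For one subject it says only: "Each subject is expected to complete the study, including all FU and Survival visits, within approximately 132 days".

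Section 11.1.1.5 gives a different end: "A FU visit will be conducted 6 weeks after the EoT visit to assess recurrence and to conduct a final safety assessment". In Table 4 of section 16.0 the row "Adverse Event Monitoring" is marked from Baseline to EoT, at the 6-Week FU and at unscheduled visits. Section 14.1 records medication given for AEs after EoT only up to the 6-Week FU. Section 12.3 asks for EoT procedures when a subject discontinues treatment, so the 6-Week FU moves earlier with an early stop.

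The Day 42 and Day 84 contacts are tied to first dose, not to EoT (15.23): "Survival will be determined on Day 42 and Day 84". Table 5 lists treatment outcome, vital status and Karnofsky score for them, and no AE monitoring. The SAP repeats both schedules as its Tables 1 and 2.

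SAP 10.3 opens its definition with "A TEAE is defined as any event not present prior to the initiation of the study treatment", adds pre-existing events that worsen, and gives no end. Its tables show the number and percentage of subjects with events by treatment group. The primary endpoint (Protocol 10.1) is the frequency of TEAEs, drug-related AEs, discontinuations due to AEs, and deaths.

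**The concern.** There are two problems, both touching the primary endpoint.

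First, sites can differ. A site working from 17.9 may ask about and record new AEs at the Day 84 contact. A site working from Tables 4 and 5 has no scheduled AE question after the 6-Week FU. SAP 10.3 would pool both kinds of record in one table.

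Second, under the schedule a subject's observation time depends on when treatment ended. A subject who stops early is watched for new AEs for fewer days than one who completes, yet each counts as one in the denominator. If one arm has more early stops, for whatever reason, its crude percentages rest on less follow-up.

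**Working it through.** **1. The plan's own duration.** Maximum treatment is 91 days (15.25) and follow-up is 6 weeks after EoT: 91 + 42 = Day 133, which is 132 days after Day 1. This reproduces the figure of about 132 days in 11.3. It is the longest planned course, not a window that every subject has.

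**2. AE window under Table 4.** Window = EoT day + 42.

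| EoT day | Last scheduled AE day | Days from there to the Day 84 contact | 133 ÷ window |
|---|---|---|---|
| 7 | 49 | 35 | 2.71 |
| 14 | 56 | 28 | 2.38 |
| 28 | 70 | 14 | 1.90 |
| 42 | 84 | 0 | 1.58 |
| 91 | 133 | 0 | 1.00 |

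For any EoT before Day 42, a contact takes place after the last scheduled AE question, and Table 5 does not ask about AEs at it.

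**3. Which results depend on the window.**
- Discontinuations due to AEs occur by EoT: unaffected.
- Mortality at Days 42 and 84 (SAP 8.2.3) is ascertained at fixed days: unaffected.
- Any TEAE: a subject who stopped for an AE already counts, whatever the later window.
- Drug-related AEs: each followed subject has 42 days off drug. At the half-life of about 20 hours in 8.1, that is 42 × 24 / 20 = 50.4 half-lives, so late related events are largely covered.
- Serious, severe, SOC/PT and leading-to-death rows, for events that did not cause the stopping: exposed. For example, a Day 70 death in a Day 14 stopper is in the Day 84 mortality count. The event behind it, if it began after Day 56, falls outside scheduled AE collection and may be missing from the table of TEAEs leading to death.

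**4. Size for an exposed row.** The documents give no stopping rates or event risks, so all of these are assumptions. Take a constant hazard, equal in both arms, for an event unrelated to stopping. Let s be the share stopping on Day 14, T the EoT day for the rest, and λ = −ln(1 − risk over 84 days)/84. Then

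P = s[1 − exp(−56λ)] + (1 − s)[1 − exp(−(T + 42)λ)].

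Worked case: 84-day risk 50%, T = 84. λ = 0.6931/84 = 0.00825. The bracketed risks are 37.0% at 56 days and 64.6% at 126 days. With s = 10%, P = 61.9%; with s = 30%, P = 56.4%. The difference is −5.5 points, or 0.6 of a subject in 11.

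Differences for s = 10% against 30%, in points:

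| 84-day risk | T = 42 | T = 84 |
|---|---|---|
| 20% | −1.2 | −2.9 |
| 50% | −2.6 | −5.5 |
| 80% | −2.8 | −5.1 |
| 95% | −1.7 | −2.5 |

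The largest difference found was −8.3 points (0.9 of 11), at 10% against 40% stopping, 50% risk and T = 84.

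**5. If the on-drug hazard is truly higher in the arm with more stops** (10% against 30% stopping, 84-day risk 30% or 50%, T = 42 or 84): a hazard ratio of 1.25 shows as −1.1 to +0.8 points, 1.5 as +2.8 to +4.0, and 2 as +7.6 to +9.7. A modest excess can be hidden; a larger one is not.

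**The case against.** A reader might infer that the primary TEAE frequencies favour the worse-tolerated arm. The documents do not support that. Step 3 of the working shows that two of the four components cannot move this way, and that drug-related events are largely covered. For any TEAE the sign reverses. Suppose 4 of 11 in one arm and 1 of 11 in the other stop on Day 14, the rest are treated to Day 84, and the 84-day risk is 30%. The risk is then 21.2% at 56 days and 41.4% at 126 days. For an equal-hazard event unrelated to stopping, the arms show (4 × 0.2116 + 7 × 0.4143)/11 = 34.1% and (1 × 0.2116 + 10 × 0.4143)/11 = 39.6%. If those subjects stopped because of an AE, each counts as an event: (4 + 7 × 0.4143)/11 = 62.7% against (1 + 10 × 0.4143)/11 = 46.8%. The arm with more intolerance then looks worse, as it should. Nor is it known which arm will have more early stops, since 12.3 also allows discontinuation for lack of efficacy.

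It can also be said that 17.9 takes in whatever subjects report or staff observe, that 17.10 requires an SAE to be reported once the site learns of it, that unscheduled visits collect AEs, and that 11.3 could be read as meaning each subject's own last visit. These provisions make later capture possible, but it would be unprompted and would vary by site. Section 17.11 follows up events already recorded and does not collect new ones.

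Finally, the study is exploratory, with no formal sample size, and SAP 10.1 summarises treatment duration, which helps a reader judge the percentages. That lowers the stakes. It does not supply a defined window or a like-for-like comparison.

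**Conclusion.** The inconsistency stands on the documents alone: two stated ends of AE collection in the protocol, one of them defined only for the trial, and none in the SAP. The scheduled window is EoT + 42 days, from 56 days for a Day 14 stop to 133 days for a 91-day course, a ratio of 2.38.

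The consequence is conditional and small. If early stopping differs by arm, crude serious, severe, SOC/PT and leading-to-death percentages, for events that did not cause the stopping, may be biased toward the arm with more early stops. In the scenarios run this is 1.2 to 5.5 points at 10% against 30% stopping and at most 8.3 points, always less than one subject of 11. Those figures rest on assumed stopping shares, a Day 14 stop and constant equal hazards. They do not show a bias in the primary endpoint as a whole or predict which arm would benefit. The change is worth making because it concerns the primary endpoint and costs little.

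**What to change.** 1. Protocol: reconcile 17.9, 15.29, the synopsis, 11.1.1.5 and Tables 4 and 5 to one per-subject end of AE collection, the later of the 6-Week FU and the Day 84 contact, and add a matching AE row to Table 5. The shortest planned window rises to 84 days and the ratio to the longest falls to 133/84 = 1.58. The effect is limited now, because enrolment stopped at 22 subjects (SAP sections 11 and 12).

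2. SAP 10.3: state the same end for TEAEs. Repeat the overall summary and the SOC/PT tables for events starting from first dose to Day 42, with a rule for incomplete start dates, and keep the all-follow-up tables as the second view. Even an EoT on Day 3 has scheduled AE collection to Day 45, so the schedule covers this window for practically every subject, barring death, withdrawal or loss to follow-up. No new data are needed, and planned follow-up is then equal between arms.

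Cost: AE questions at contacts that already take place, a sentence in each document and one more table set. The Day 42 view will show fewer events and will miss later ones, which is why the full tables stay.

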17.10 Serious Adverse Event Reporting Requirements

All SAEs must be reported within 24 hours of the site becoming aware of the SAE. Any event that is serious, study drug-related, and unexpected as assessed by the medical monitor or the Sponsor will be submitted to the regulatory authorities in accordance with national regulatory laws and regulations. The PI will be responsible for reporting all SAEs that require reporting to the local Institutional Review Board/Ethics Committee (IRB/EC) in accordance with its regulations and guidelines.

17.11 Adverse Event and Serious Adverse Event Follow-up

All AEs and SAEs will be followed up to resolution (the subject's health has returned to her baseline status or all variables have returned to normal) or until an outcome is reached, stabilization occurs (the investigator does not expect any further improvement or worsening of the event) or the event is otherwise explained, regardless of whether the subject is still participating in the study. All appropriate therapeutic measures should be undertaken and recorded. Where appropriate, medical tests and examinations will be performed to document resolution of the event(s).

17.12 Serious Adverse Event Reporting – Procedures for Investigators Initial Reports and Follow-Up SAE Reports:

To report an SAE, the SAE eCRF form within the Electronic Data Capture (EDC) system must be completed. All SAEs, whether or not deemed drug-related or expected, must be reported by the investigator or qualified designee within 24 hours of first becoming aware of the event. The investigator/qualified designee will enter the required information regarding the SAE into the appropriate form, which will automatically result in distribution of the information to the appropriate Sponsor contact.

17.13 Procedures for Emergency Unblinding

This is a double-blind study. The investigator should only be unblinded if this information is necessary to determine treatment of an emergency. The Interactive Web Response Systems (IWRS) can provide the information necessary to unblind the investigator, in case of an emergency. In the event that the web-based IWRS system is not available, emergency unblinding can occur by contacting the formation help-desk as follows:

18.0 Data Collection, Study Monitoring and Record Management

18.1 Data Collection and Reporting

Data for this study will be collected using eCRFs. The investigator and study site staff will receive training regarding the completion of the eCRF. Visit-specific data should be entered into the eCRF and be ready for review as soon as possible, but no later than 5 days after each visit/time point.

All protocol-required information collected during the study must be entered by the investigator or designated representative in the source documents and eCRF. All data entry, modification or deletion will be recorded indicating the individual subject, original value, the new value, the reason for change, who made the change, and when the change was made. All data changes will be clearly indicated with a means to locate prior values. The investigator will maintain a list of individuals who are authorized to enter or correct data on the eCRFs.

The investigator or designated sub-investigator, following review of the data in the eCRF, will confirm the validity of each subject's data by signing the eCRF.

18.2 Study Monitoring

Study progress will be monitored by the Sponsor or its representative as frequently as necessary to ensure adequate and accurate data collection, protocol compliance, and

study conduct in accordance with accepted regulatory requirements. The PI must make all the subject data available to the monitor for review during the planned site monitoring visits. Arrangements for monitoring visits will be made in advance, except in emergency cases.

18.3 Investigator Study Files

The PI is responsible for maintaining all study-related documents in study files. The Sponsor will notify the PI when retention of study files is no longer necessary. The following documents will be kept in the study files or be readily accessible:

- original protocol and all amendments;
- signed agreement or protocol;
- signed and dated study staff roles and responsibilities log;
- copy of the current *curriculum vitae* of the PI and of all sub-investigators;
- IRB/EC membership list and all IRB/EC approvals for the protocol and amendments, informed consent documentation and all updates, advertisements, and written information provided to subjects; all IRB/EC correspondence; documentation that the IB and subsequent revisions have been submitted to the IRB/EC; documentation that all SAEs and any periodic safety reports have been submitted to the IRB/EC; and annual IRB/EC renewals (as required);
- updated laboratory certification and the laboratory's normal values (covering the entire time interval of the study for all laboratory tests conducted during the study);
- all confirmations of investigational drug receipt, drug accountability logs and drug return records;
- a CD or DVD containing final subject eCRF data;
- all correspondence to or from the Sponsor or its designees;
- blank informed consent form;
- Investigator's Brochure;
- subject screening log;
- subject list (contains subject initials and/or protocol-specific subject number);
- all subjects' original signed informed consents; and,
- monitoring visit log.

18.4 Retention of Records

Essential documents should be retained until at least 2 years after the last approval of a marketing application and until there are no pending or contemplated marketing applications, or at least 2 years have elapsed since the formal discontinuation of the clinical development of the investigational product. These documents should be retained for a longer period, however, if required by the applicable regulatory requirements or by an agreement with the Sponsor.

The Sponsor will inform the PI/institution in writing of the need for record retention and will notify the PI/institution in writing when the trial-related records are no longer needed.

An investigator who withdraws from the responsibility of maintaining study records or wishes to move them to a new location has the obligation to place them in safekeeping and to inform the Sponsor of their location.

